### **3.0 Background**

*3.1 Summarize the relevant prior research on this topic and gaps in current knowledge within the field of study:*

Dysbiosis of the gut microbiota, characterized as adverse changes in the abundance and/or composition of gut microbes, has been implicated in pathophysiology of a number of chronic diseases including neurological disorders, colitis, atherosclerosis, and metabolic diseases. Several lines of evidence in both animal models and humans also implicate gut dysbiosis in the etiology of insulin resistance and T2D. Future studies are needed to understand the potential link between gut microbial composition and function with glucose homeostasis and risk of T2D. Recently, gut microbiota-generated increases in TMAO has become a novel target for the treatment of cardiovascular diseases. The results of studies in rodent models indicate a causal role of TMAO in the development of atherosclerosis and several meta-analyses support a dose-dependency of TMAO in predicting adverse CVD events. Given the close relationship between T2D and cardiovascular disease, perhaps it is not surprising that a higher prevalence of T2D has been observed in populations with elevated TMAO. The potential role of TMAO in the development of insulin resistance and T2D is supported by multiple observations. Changes in gut microbial composition with aging are observed even in the absence of overt disease. However, the role of these changes on the reduced glucose homeostasis observed with aging is unknown. Interestingly, TMAO increases with advancing age in both mice and humans. Human TMAO increases are believed to be a consequence of changes in the gut microbiota, i.e., dysbiosis. Indeed, there is an increase in the abundance of TMA-producing bacteria with aging. Importantly, and as emphasized earlier, plasma TMAO concentrations are dependent on the composition of the gut

microbiota and higher baseline TMAO concentrations are associated with larger increases in TMAO with choline loading. As such, we hypothesize that older adults will demonstrate greater gut microbiota generated increases in TMAO following choline loading compared with young adults. Furthermore, the greater gut microbiota-generated increases in TMAO following choline loading will be associated with not only a greater abundance of TMA-producing bacteria but a larger decrement in insulin sensitivity, mixed meal glucose tolerance, and a reduction in 24-hr glycemic control.

*3.2 Describe any relevant preliminary data:*

N/A

*3.3 Based on the existing literature, provide the scientific or scholarly rationale for and significance of your research and how will it add to existing knowledge:*

The premise of the present proposal is that: 1) advancing age is associated with increases the abundance of TMA producing bacteria and TMAO concentrations; 2) older adults are at increased risk of insulin resistance, glucose intolerance, and T2D; and 3) there is accumulating evidence that elevated TMAO levels are predictive of, and contributory to, risk of T2D; and 4) the impact of gut microbiota-generated increases in TMAO on age-related changes in glucose homeostasis is unknown. Our proposal has significant translational potential as our findings will advance basic science findings in mouse models to determine relevance in humans and provide novel mechanistic insight into meta-organismal nutrient metabolism as a basis of age-related reductions in glucose homeostasis. One of the major challenges in understanding this link is the potential confounding influence of habitual dietary intake on key outcome variables. We will overcome this limitation by leveraging our existing expertise in rigorously standardizing participant diets to isolate the effects of meta-organismal metabolism of dietary choline as a basis for elevated risk of T2D with advancing age using state-of-the-art and reproducible methodology. Furthermore, our study will provide important insight into the gut microbiota as an important source of variability in glucose metabolism to TMAO. Our findings could have important policy and clinical implications. If modifying the gut microbiota to reduce age-related T2D risk is prudent, then clinical practice could be advanced by informing treatment guidelines and by providing rationale for individualizing nutritional or pharmaceutical interventions that target the gut microbiota as the interface between TMAO and T2D risk.

## **4.0 Study Endpoints**

4.1 *Describe the primary and secondary **study** endpoints. See links below for discussion of study endpoints and how they may differ from study objectives. These are most common in clinical trials but are sometimes applicable to other types of biomedical research, as well as social, behavioral, or educational research. See link below for a discussion.*

[https://docs.google.com/document/d/1Wocz7K7a0hCQJPPO\\_khh511SQjhGDDGHzcOPRHR5Tw/edit?usp=sharing](https://docs.google.com/document/d/1Wocz7K7a0hCQJPPO_khh511SQjhGDDGHzcOPRHR5Tw/edit?usp=sharing)

With this study, there are three continuous measurements which will define our study endpoints. These include oral glucose tolerance, flow mediated dilation of the brachial artery and aortic pulse wave velocity measurements corresponding to arterial stiffness and a mixed meal tolerance test.

With regards to our hypothesis stated in section 2.2, our study endpoints will be as follows: Gut microbiota-generated increases in plasma TMAO will be greater in older compared with young adults and this will be associated with a correspondingly greater reduction of insulin sensitivity, mixed meal tolerance, and 24-hr glycemic control in older adults.

4.2 *Describe any primary or secondary **safety** endpoints. These should be included for all studies that are greater than minimal risk. (Minimal risk: The probability and magnitude of harm or discomfort anticipated in the research that are not greater in and of themselves than those ordinarily encountered in daily life or during the performance of routine physical or psychological examinations or tests.):*

Our safety endpoints will correspond to the potential risks that subjects may experience which are stated in section 17.1.

Potential safety endpoints which could occur with this study are as follows: 1) Any severe GI distress or complaints reported with consumption of the choline or placebo supplement, 2) Discomfort or pain which is not tolerated by the subject with blood draws, 3) Discomfort and pain due to the inflation of the BP cuff on the forearm of the participant; and 4) Discomfort which is reported when measuring arterial stiffness measurements due to slight pressure being applied to the carotid, brachial, radial and femoral arteries.

## 5.0 Study Design and Statistical Analysis Plan

5.1 *Describe the basic study design/approach (e.g., qualitative study using five focus groups of first year students to describe assimilation into the university community; randomized controlled trial of a behavioral change*

*intervention to increase dietary intake of whole grains; pre- post-test evaluation of new pedagogical techniques to improve adult literacy):*

A double-blind randomized 2x3 crossover design with 3 repeated measures in each period will be used. Pre-/post-test evaluation used in each period to evaluate the ingestion of choline/placebo on the effects to cardiometabolic health.

**5.2** *Describe corresponding data analysis plan/approach (e.g., content analysis of focus group transcripts; descriptive analysis followed by linear regression modeling; nonparametric analysis of pre- and post-test measures):*

Data will be examined for the presence of outliers, violations of normality and missing data. Major violations of normality will be corrected with an appropriate transformation procedure. In case of an outlier, rather than transform the data, the outlier will be “Winsorized”, that is, replaced by the most extreme value in the tail of the distribution. Data will be checked for sequence, period and carryover effects. Next, a mixed-effects linear model (using SAS PROC MIXED) will be used to estimate the treatment differences between choline and placebo ( $H_0: \mu_{AB} - \mu_{BA} = 0$ ). Because of the two repeated measurements of the dependent variable in each period, we will treat the multiple observations as nested within individuals. This will allow us to model the various sources of intra-person and inter-person variability, as well as account for the correlation in the nested data to make the correct inference regarding differences between treatments. Confidence intervals (95%) and bootstrapped standard error estimates will be reported for statistical precision and estimation of effect sizes for a larger more comprehensive trial. An identical approach will be used for analysis of other outcomes (e.g., arterial stiffness, etc.).

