## 2.0 Objectives

### 2.1 Describe the purpose, specific aims, or objectives of this study:

To establish proof-of-concept for a greater reduction in glucose homeostasis following increases in gut microbiota-generated TMAO on glucose homeostasis in older compared with young adults in order to conduct a larger, more comprehensive and mechanistic trial in the future.

*2.2 State the hypotheses to be tested:*

We hypothesize that gut microbiota-generated increases in plasma TMAO will be greater in older compared with young adults and this will be associated with a correspondingly greater reduction of insulin sensitivity, mixed meal tolerance, and 24-hr glycemic control in older adults.

In addition, we hypothesize that the magnitude of change in gut microbiota-generated increases in TMAO and measures of insulin sensitivity, mixed meal tolerance, and 24-hr glycemic control with the intervention will be associated with the magnitude of change in the abundance of TMA-producing bacteria and/or expression of cutC TMA lyase.

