## 14.0 Number of Subjects

14.1 *Indicate the total number of subjects to be enrolled and how this number was determined (e.g., sample size calculation [show], number of available subjects in a finite pool, number of tests funding award would allow):*

We have powered our pilot study to detect a change in insulin sensitivity of  $20 \pm 32\%$  (effect size=0.63). We believe changes in other outcomes will be of similar magnitude. We will enroll 60 participants. Importantly, the purpose of this pilot study is to assess feasibility, acceptability, and provide proof of concept. Even with a small sample size (n=60), a cross-

over design with 4 repeated measures will give us fairly good estimates of the effect sizes, which is needed for a more comprehensive future trial.

*14.2 If this is a multi-site study, indicate the number of subjects to be enrolled at this site and the total to be enrolled from all sites:*

N/A

*14.3 If applicable, indicate the number of potential subjects you expect to screen for enrollment, and the number of subjects you will need to complete the research procedures:*

300-400 potential subjects will be screened for eligibility in this study. Of this 300-400 individuals, 60 participants who are eligible will be enrolled to take part in the investigation.

*14.4 If the study has more than one procedure, indicate the total number of subjects to undergo each procedure separately:*

All subjects will complete each procedure.

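### Section 5.2 leaves the analysis scale to be chosen from the data, while the older-versus-young objective can turn on whether change is absolute or relative

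*Combined protocol and SAP*

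**What the plan says.** Section 5.2 begins with a look at the data: "Data will be examined for the presence of outliers, violations of normality and missing data". It then states that "Major violations of normality will be corrected with an appropriate transformation procedure". No test, threshold or transformation is named. It does not say whether outcomes, changes or residuals are checked, or whether the check is blind to treatment. A second rule follows: "In case of an outlier, rather than transform the data, the outlier will be" Winsorized. The mixed model in 5.2 estimates choline against placebo only, and the same approach is applied to the other outcomes.

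The primary objective (1.0 and 2.1) is "To establish proof-of-concept for a greater reduction in glucose homeostasis following increases in gut microbiota-generated TMAO on glucose homeostasis in older compared with young adults". Section 2.2 adds: "We hypothesize that gut microbiota-generated increases in plasma TMAO will be greater in older compared with young adults". Section 4.1 repeats this as the endpoint. None of these places says whether greater is meant in absolute or relative terms.

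On baselines, 3.1 says that "TMAO increases with advancing age in both mice and humans" and that "higher baseline TMAO concentrations are associated with larger increases in TMAO with choline loading". Section 3.3 has older adults at higher risk of insulin resistance. Section 14.1 reads "We have powered our pilot study to detect a change in insulin sensitivity of" 20 ± 32%, which is a percent change, but nothing links that to the analysis scale. No section fixes a scale for any outcome.

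**The concern.** For choline against placebo alone, a monotone transformation alters size and precision but seldom direction. A comparison of response size between two groups is different. If the groups start at different levels and the treatment moves the outcome, a difference can be present on one scale and absent, or even reversed, on another. The protocol expects both conditions.

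Under 5.2 the scale follows from an unspecified judgement about normality. The outlier clause can pull the other way, because one long right tail may be read as non-normality (transform) or as outliers (Winsorize and stay raw). At stake are the answer to the primary objective and the effect sizes that the pilot is meant to supply to a larger trial, which could end up on different scales for different outcomes for reasons unrelated to the question.

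**Working it through.** **The plan's own figure.** 20/32 = 0.625, which agrees with the stated 0.63. It shows that 14.1 thinks in percent change. The sample size plays no further part here.

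**Algebra.** Let P be the mean under placebo and f the fold change under choline, the same in both age groups.
- Raw contrast: (f − 1)·P(older) − (f − 1)·P(young) = (f − 1)·[P(older) − P(young)]. It is non-zero whenever f ≠ 1 and baselines differ.
- Log contrast: ln f − ln f = 0.

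**Examples (assumed values).**

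| Case | Young | Older | Raw change | Relative change |
|---|---|---|---|---|
| TMAO, same fold | 3 to 6 | 6 to 12 | +3 v +6 | ×2 v ×2 |
| TMAO, reversal | 2 to 5 | 5 to 9 | +3 v +4 | ×2.5 v ×1.8 |
| Insulin sensitivity, same 20% fall | 6 to 4.8 | 4 to 3.2 | −1.2 v −0.8 | −20% v −20% |

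The second row is greater in older adults on one scale and greater in young adults on the other. In the third, the raw scale makes the fall look smaller in older adults.

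**TMAO simulation.** From the documents: 60 participants. Assumed, because the documents give no baselines or SDs: 30 per age group; both groups double; older baseline 1.33, 1.5 or 2.0 times young; two-sided 5%. For strongly skewed data: baseline log-SD 0.4-0.8, response log-SD 0.4, measurement log-SD 0.25. The test is a t-test between age groups on each person's choline-minus-placebo difference.

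| How the scale is set | Age difference declared |
|---|---|
| Log, preset | about 5% |
| Shapiro-Wilk at 0.05 on raw residuals, strongly skewed | 4-9% (log chosen in 96-99.9% of trials) |
| Absolute skewness above 1, strongly skewed | 5-17% |
| Shapiro-Wilk, less skewed data | 20-39% |
| Winsorize and stay raw | 26-72% |

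The last two rows depend on unstated choices. A Winsorized range of that size arises when outliers are flagged within each age group (a 1.5 interquartile-range fence). Flagged across both groups pooled, Winsorizing leaves the rates close to plain raw analysis, which runs from 9% to 62%. The less-skewed range needs log-SDs of roughly 0.2. A separate simulation used before and after values in each period, with between-person log-SD 0.3 and within-person log-SD 0.2. With Shapiro-Wilk choosing the scale and a doubling in both groups, it declared the rise greater in older adults in 11%, 28% and 34% of runs at baseline ratios 1.25, 1.5 and 2.0. Preset log gave 2-3% in that direction.

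**Insulin sensitivity simulation.** Assumed: a fall of 10% in young and 30% in older adults, older baseline 0.6-0.8 of young, baseline log-SD 0.4, response log-SD 0.3.

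Check of the log-scale power: the effect is ln(0.9/0.7) = 0.251.
- No measurement error: 0.251/0.3 = 0.838; 0.838 × √15 − 1.96 = 1.28; power about 90% by the normal approximation.
- Measurement log-SD 0.25: SD = √(0.09 + 2 × 0.0625) = 0.464; 0.251/0.464 = 0.542; 0.542 × √15 − 1.96 = 0.14; power about 55%.

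| Measurement log-SD | Preset log | Shapiro-Wilk picks | Raw |
|---|---|---|---|
| 0 | 88-89% | 71-76% | 34-61% |
| 0.25 | about 55% | about 46% | 17-30% |

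**The case against.** Several points on the other side stand.

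- **Always-raw against always-log is not a test of the rule.** A reader might take the raw rates at a doubled baseline, 36-62%, as the error rate of 5.2. They are not. With data that skewed, a formal normality test nearly always moves the analysis to logs, and the rate falls to 4-9%. The higher rates need milder skew or the outlier clause.
- **A larger absolute rise is not necessarily a false positive.** Section 3.1 derives the age hypothesis from larger increases at higher baselines. An absolute reading of greater is therefore natural, and a raw analysis that detects such a rise would be correct under it. Section 3.1 also does not say that the response is proportional; that is one reading of it.
- **Section 5.2 contains no older-versus-young test.** The scale rule acts on a comparison that has yet to be written into the model. The missing term is the larger gap.
- **The percent change in 14.1 does not require logs.** Percent change and log change are not the same quantity.
- **This is a pilot**, with 95% intervals and bootstrapped standard errors promised, and normality-triggered transformation is common practice.

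These limit the size of the point without removing it. Section 5.2 names no formal test, so the reassuring 4-9% cannot be assumed. Once an age-by-treatment term is added, its answer will depend on a scale that nobody has fixed. Pilot status is a weak defence when a stated purpose is to supply effect sizes for the next trial.

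**Conclusion.** The point holds as a should-fix matter and a cheap improvement. The algebra and examples show that the older-versus-young answer can change with the scale, and 5.2 leaves the scale to be decided from the data under two competing rules. How often this would matter cannot be derived from the documents. Under the assumed TMAO inputs it ranges from almost no effect (4-9% against about 5%) to a large one (20-39%, or 26-72% with Winsorized raw data). For insulin sensitivity, letting a test choose the scale costs about 9 points of power with measurement error (55% to 46%) and about 12 to 18 without it (88-89% to 71-76%).

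Three stronger inferences are not supported: that the normality rule itself produces errors in 36-62% of trials, that a raw-scale finding of a greater rise is wrong, and that the documents oblige the investigators to use logs. The TMAO rates are errors only if greater means relative change.

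**What to change.** Before unblinding, amend 2.2 and 5.2 as follows.

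1. For each outcome, state whether greater means absolute or relative change. The choice is the investigators'.
2. Fix the scale to match: natural log for TMAO and insulin sensitivity if relative, with the older-to-young ratio of choline/placebo ratios as the estimate; raw units if absolute. Logs would be consistent with the percent change in 14.1.
3. Add age group and age-by-treatment to the mixed model, so that the scale applies to a stated comparison.
4. Keep residual checks, done blind to treatment code, as diagnostics that do not change the scale. Use bootstrap intervals if residuals are non-normal.
5. Report the other scale as a sensitivity analysis.

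Cost: a few sentences and one extra table. If the relative scale is chosen, the main estimates become ratios, and absolute changes move to the second table.

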## 12.0 Inclusion and Exclusion Criteria

*12.1 Describe how you will screen individuals for eligibility. When will screening occur and what procedures will you use? Upload any screening scripts or surveys to Protocol Management:*

Those who respond to the investigation's advertisements will be asked to complete a brief online screening questionnaire to confirm basic eligibility criteria on Qualtrics (e.g., age, health status).

Furthermore, subjects will be screened for any possible health problems that would make it unsafe to participate, they will be required to complete a medical history questionnaire and made fully aware of their right to withdraw from the study at any time.

*12.2 Describe the eligibility criteria that define who will be included and who will be excluded from enrollment for each procedure of your study.*

*Include any geographic criteria (e.g., Virginia Tech undergraduate students, a national sample of adults with engineering degrees, minors aged 8-12 in the New River Valley, university faculty in Virginia and Paris, France):*

Inclusion criteria is as follows:

- 18-79 years of age
- Sedentary (low physical activity)
- Not diabetic
- Not taking medications that influence the study results
- Not have severe obesity (BMI <35kg/m^2)
- Non-smokers
- Not pregnant
- Without any major medical problems

- Fully vaccinated against COVID-19. Individuals are fully vaccinated 2 weeks after their final dose of an approved vaccine.

Exclusion criteria would be if individualss do not fall under any of the above criteria.

Therefore, subjects will be excluded if they are not between 18-79 years of age, pregnant, a smoker, have a BMI  $>35 \text{ kg/m}^2$ . Additionally, if they have changed their dietary patterns in the last month, have unstable heart disease or diabetes, vegetarians, vegans, untreated high cholesterol, or have health problems that make it unsafe to participate

*12.3 Indicate specifically whether you will include or exclude each of the following special populations: (You may not include members of these populations as subjects in your research unless you indicate them in the description of your subject population.)*

- *Minors, as defined by state law where the study is performed (infants, children, teenagers)*
- *Pregnant women (can be included in minimal risk studies by mentioning in section 13.1)*
- *Prisoners (including all incarcerated individuals)*
- *Adults not capable to consent on their own behalf*

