## 26.0 Resources Available

26.1 *Describe the resources available to conduct the research. For example, as appropriate:*

- *Describe the PI’s availability to supervise the research.*

- *Justify the feasibility of recruiting the required number of suitable subjects within the agreed recruitment period. For example, how many potential subjects do you have access to? What percentage of those potential subjects do you need to recruit?*
- *Describe the time that you will devote to conducting and completing the research.*
- *Describe your facilities.*
- *Describe the availability of medical or psychological resources that subjects might need as a result of an anticipated or unanticipated consequence of participation in the research.*
- *Describe your process to ensure that all persons assisting with the research are adequately informed about the protocol, the research procedures, and their duties and functions (e.g., training plans, detailed study notebooks).*

- The PI commits 70% of his effort to research activities so is broadly available and in the laboratory on a daily basis.
- We have powered our pilot study to detect a change in FMD  $1.0 \pm 1.5\%$ . The purpose of the pilot study is to assess feasibility, acceptability, and provide proof of concept. Even with a small sample size ( $n=60$ ), a crossover design with repeated measures will give us fairly good estimates of the effect sizes, which is needed for a more comprehensive future trial.
- The PI has a 20+ track year record (15 years at Virginia Tech) recruiting and studying participants for studies similar to these. We typically need to screen 10 individuals for every 1 participant enrolled.
- The PI oversees a laboratory with a clinical coordinator and 5-6 graduate students. He is in the laboratory on a daily-basis working with students and is involved in data collection.

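### The primary question is older versus young, but the planned model has no age term, the age groups are undefined, and n=60 is justified only for an overall change

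*Combined protocol and SAP*

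**What the plan says.** **Objective and endpoints.** Section 2.1 seeks proof of concept for a "greater reduction in glucose homeostasis following increases in gut microbiota-generated TMAO on glucose homeostasis in older compared with young adults". The first hypothesis in 2.2 makes the same comparison. Section 4.1 repeats it as the endpoint statement: the TMAO rise will be greater in older adults and "this will be associated with a correspondingly greater reduction of insulin sensitivity, mixed meal tolerance, and 24-hr glycemic control in older adults".

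**Analysis.** Section 5.2 specifies checks for sequence, period and carryover, then a mixed-effects model that "will be used to estimate the treatment differences between choline and placebo". Its null hypothesis is written on that difference alone, and the same approach is extended to the other outcomes. Neither 5.1 nor 5.2 mentions age.

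**Population.** Section 12.2 admits people "18-79 years of age". No cut-point, group size, ratio or stratification by age appears anywhere.

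**Sample size.** Section 14.1: "We have powered our pilot study to detect a change in insulin sensitivity" of 20 ± 32%, effect size 0.63, with 60 enrolled. Section 26.1, for the same 60: "We have powered our pilot study to detect a change in FMD" of 1.0 ± 1.5%. Neither mentions age.

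**Design description.** Section 5.1: "A double-blind randomized 2x3 crossover design with 3 repeated measures in each period will be used", followed by "Pre-/post-test evaluation used in each period". Section 5.2 speaks of two measurements per period, section 14.1 of four, and the section 1.0 summary of a 2 x 4 design.

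**The concern.** An older-versus-young difference in the choline effect is an interaction. A model with only a treatment term estimates the average effect over whoever was enrolled and does not address it. With the age groups also undefined, the cut-point, the handling of people in the middle of the range and the model term would all be chosen after the data are seen.

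The study's deliverable is effect sizes for a larger trial (1.0, 5.2, 14.1). An unplanned age contrast, or one taken from the wrong model term, would carry over into that trial's design. The word *powered* in 14.1 and 26.1 could also lead a reader to think the primary objective is covered.

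The unclear repeated-measures structure adds to this, because it decides which model term carries the age contrast. If pre and post values both enter as outcomes and no time factor is included (5.2 names none), the treatment term averages them and shows half of the effect on change. A plain age-by-treatment term is halved in the same way.

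**Working it through.** **Inputs from the documents.** n = 60; insulin sensitivity change 20 ± 32%; FMD change 1.0 ± 1.5%. The ± is read as an SD because 20/32 = 0.625, which matches the stated 0.63.

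**Assumed, because not stated.** Two-sided alpha 0.05, 30 older and 30 young, equal SD in both groups, no dropout. The meaning of the 32 is also open, so two readings are carried (units are percentage points of change):
- (A) 32 is the SD of the choline-minus-placebo change.
- (B) 32 is the SD of the change within one period and the periods are uncorrelated, so the SD of the difference is 32 × √2 = 45.3.

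**Step 1: the plan's own claim.** One-sample t test, noncentrality (20/SD) × √60. Power is 99.7% (A) or 92% (B). For FMD, 1.0/1.5 = 0.667 and power is 99.9%, reading 1.5 as the SD of the difference. So 60 is ample for an overall change.

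**Step 2: the age difference.** Two-sample t test on each person's choline-minus-placebo change. Standard error = SD × √(2/30); half-width = t(58) × standard error, with t(58) = 2.002.
- (A) SE = 32 × 0.2582 = 8.26; half-width 16.5.
- (B) SE = 45.25 × 0.2582 = 11.68; half-width 23.4.

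| | (A) SD 32 | (B) SD 45.3 |
|---|---|---|
| Age difference with 80% power, 30/30 | 23.5 | 33.3 |
| 95% CI half-width, 30/30 | 16.5 | 23.4 |
| Power if the age difference is 20 points | 66% | 39% |
| Age difference with 80% power, 20/20 | 29.1 | 41.1 |
| 95% CI half-width, 20/20 | 20.5 | 29.0 |

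The 20/20 rows suppose that a third of the 60 fall between the two age groups.

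**Step 3: what those differences mean.** Hold the overall change at 20 points. A difference of 23.5 then means 20 ± 23.54/2, about 31.8 in older and 8.2 in young adults. Under (B), 20 ± 33.29/2 gives about 36.6 and 3.4.

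**Step 4: between-period correlation.** With SD = 32 × √(2(1 − r)), the difference detectable with 80% power is 28.8 points at r = 0.25 (SD 39.2), 23.5 at r = 0.5 (SD 32) and 16.6 at r = 0.75 (SD 22.6).

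**Step 5: which model term.** With randomised order the treatments do not differ at the pre-period measurement (0), and they differ by 20 at the post-period measurement. Pooling gives (0 + 20)/2 = 10; the change contrast gives 20. In a simulation of 4,000 trials (30/30, true effects 10 in young and 30 in older, SD of the difference in change 32):
- pooled treatment term: 10.0, against a true overall effect of 20;
- pooled age-by-treatment term: 10.0, against a true age difference of 20;
- age difference in change, which equals age by treatment by time: 19.7;
- age difference in post value adjusted for pre value: 19.8.

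**Step 6: repeated measures against the schedule.** In 8.2 the glucose tolerance test falls at sessions 2, 8, 11 and 17, that is, before and after each period: two per period, four in total. This agrees with 5.2 and 14.1. The three per period and the 2x3 label in 5.1 fit only the three testing days in each block.

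**The case against.** The strongest reply is that this is a proof-of-concept pilot. Sections 14.1 and 26.1 say its purpose is feasibility, acceptability and effect-size estimates, so low power for an interaction is expected. That stands, and it is why the sample size is not criticised. It does not excuse leaving the contrast in the primary objective out of the analysis plan.

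Other points have some force:
- The halving is conditional. Section 5.1's pre-/post-test wording suggests that change is intended; 5.2 is ambiguous rather than shown to be biased.
- Two per period and four in total agree with each other, so 5.1 is the outlier. The count also varies by outcome: blood pressure and body mass are measured at the weekly supplement visits too.
- The documents say a change, not an overall change. The reading is still fair, since neither statement names a group comparison.
- No dropout is optimistic. At 24 per group (20% loss, assumed) the half-width is 18.6 (A) or 26.3 (B).
- The hypothesis also links the TMAO rise to the glucose response. The age contrast is necessary but is not the whole of it.

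None of these supplies an age term or a definition of the groups.

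**Conclusion.** The concern holds and should be fixed. The absence of an age term, of age-group definitions and of any age comparison in the two power statements is plain from the text and needs no assumption. Its size depends on the assumed split, alpha, completeness and meaning of the 32. Across readings (A) and (B), the smallest age difference with 80% power at 30/30 is larger than the whole 20-point change used for sizing; it falls below 20 only with strong between-period correlation, such as 16.6 points at r = 0.75. Limited power is acceptable in a pilot. An unplanned primary contrast is not, nor is a power claim that appears to cover it.

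**What to change.** Keep n = 60 and make these changes:

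1. **12.2 or 14.1:** define the older and young groups and the planned number in each.
2. **5.2:** make the older-minus-young difference in the choline-minus-placebo pre-to-post change the analysis of the primary objective, reported with its 95% CI. Fit age group by treatment on each period's change score, or on the post value adjusted for that period's pre value. If pre and post both stay as outcomes, use age group by treatment by time for this contrast and treatment by time for the overall effect. Carry the contrast to the other outcomes and name plasma TMAO among them. The TMAO-to-glucose association in 2.2 needs its own analysis.
3. **1.0, 5.1, 5.2 and 14.1:** reconcile the design labels and repeated-measures counts with the session schedule.
4. **14.1 and 26.1:** name one sizing outcome, say what the ± is, and align or delete the FMD sentence. Possible wording for 14.1, under reading (A):

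> The sample of 60 is powered for the overall choline-minus-placebo change in insulin sensitivity (20 points, SD 32 for that difference, two-sided alpha 0.05). The older-versus-young difference will be estimated with a 95% CI (half-width about 16.5 points with 30 completers per group) and is not claimed as powered.

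If 32 is one period's SD, restate the half-width with the assumed between-period correlation (23.4 at zero).

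**Cost:** wording and model terms only, with no new subjects or measurements. The power statement becomes less favourable for the age contrast. Defining groups may require recruitment targets by age, or leave mid-age participants out of that contrast.
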